## Memorial Sloan-Kettering Cancer Center IRB Protocol

**IRB#: 08-155A(8)**

We will consider the results of this feasibility study to suggest that WEBCORE is a strategy warranting larger scale evaluation if approximately 80% of enrolled patients login to WEBCORE at least four times from the time of enrollment until six weeks following surgery. Patient assessment of the usefulness of WEBCORE will be measured via an exit survey. Clinician perceptions of the potential value of WEBCORE will be evaluated via an email survey and questions asked at a team meeting. Reasons for patient non-compliance will be assessed via results of the backup telephone calls to those who failed to login, and with the exit survey.

Potential benefits of this use of the WEBCORE platform in this context will be assessed by measuring the number and type of clinical interventions made in response to WEBCORE alerts, and by analyzing patient use of WEBCORE in relation to dates of surgery and development of documented post-surgical complications.

### **4.1.2 Patient Accrual**

This pilot study will be undertaken in patients undergoing laparotomy for presumed or confirmed gynecologic malignancy at MSKCC. Approximately 80% of all laparotomies on the gynecology service are performed for endometrial or ovarian cancer, split relatively evenly between the two (internal data). We anticipate a similar representation in our study population. We will enroll the first 5 patients of 110 patients as a small pilot to identify potential problems and correct any issues that may arise. After the evaluation of the first 5 patients the accrual period will remain open until at least 80 evaluable patients are enrolled.

### **4.1.3 Study Period**

**Duration:** For each patient, we will define a study interval beginning on the day of the pre-operative consent when the baseline questionnaire is performed, until the exit patient satisfaction interview takes place, which will be 6-8 weeks following the operative date.

**Justification:** There is no absolute definition of the post-operative period, although the Agency for Healthcare Research and Quality (AHRQ) [44] and the Surgical Care Improvement Project (SCIP) [45] generally set patient safety goals for the 30 day period following surgery. At Memorial Sloan-Kettering Cancer Center, post-operative complications are defined as those events occurring within 30 days of surgery [46], and the gynecology service has prospectively tracked and graded surgical complications for the last several years. We chose to have patients report symptoms up to and including the sixth week post-operatively because the duration of the post-operative period is poorly defined, and there may be value to the data we collect beyond 30 days. We expect to see an improvement in patients' scores on the EORTC QLQ-30, and the individual items from the CTCAE by the end of the reporting period (6 weeks).

**Memorial Sloan-Kettering Cancer Center  
IRB Protocol**

**IRB#: 08-155A(8)**

**4.2 Intervention**

Descriptions of the specific instruments are available in Section 7, and the instruments themselves are available in the appendices.

**Table 3: List of Interventions**

Instrument	Method of Administration	Population	Evaluates
European Organization for Research and Treatment of Cancer QLQ-C30 (Appendix 4)	WEBCORE	Patients	HRQL, specific post-operative symptoms
Common Toxicity Criteria (Appendix 3)	WEBCORE	Patients	Urinary symptoms, wound symptoms
Baseline Patient Information Questionnaire (Appendix 1)	Paper	Patients	Demographics, computer knowledge
Patient Satisfaction Interview (Appendix 2)	WEBCORE	Patients	Satisfaction with WEBCORE
Nurse Intervention Report (Appendix 5)	Email	Clinic Nurses	Response(s) to automated email alerts
Clinician Survey (Appendix 8)	Email	Clinic Nurses	Satisfaction with WEBCORE
Clinician Exit Meeting Questions (Appendix 6)	Focus Group	Physicians, Nurses, Session Assistants	Satisfaction with WEBCORE

**4.2.1 The Online Platform**

This design consists of a homepage for patients to login to WEBCORE, followed by screens containing a single question on each page. This design was refined through usability testing at MSKCC.

**4.2.1 Patient Training Sessions**

At the time of enrollment, each subject will undergo a 10-minute training session for the WEBCORE system on an Internet-enabled computer. This training session will be conducted by the clinical research fellow coordinating this study or a designated RSA/session assistant using a computer located in a private

**Memorial Sloan-Kettering Cancer Center  
IRB Protocol**

**IRB#: 08-155A(8)**

patient computing area on the 6th floor of the MSKCC 53rd street outpatient clinic

## Memorial Sloan-Kettering Cancer Center IRB Protocol

**IRB#: 08-155A(8)**

building. The designated RSA will be trained by the research fellow before training the enrolled subjects. A wall-mounted touch-screen computer has previously been installed in a private area on this floor for 04-020 which may be used, or a wireless touch-screen laptop may be brought to the patient in a private area. Training will be identical to the training in currently open WEBCORE studies, and will include:

- Provision of a unique username/password and URL for WEBCORE.
- Instruction on how to navigate to the WEBCORE data entry frontpage using the Internet.
- Instructions on how to login to WEBCORE, enter personal information about symptoms and quality of life.
- Instructions that information entered into WEBCORE will not be reviewed by MSKCC personnel in real-time. It will be clearly stated during training that WEBCORE cannot be relied upon as a means of communicating information to clinicians. Patients will therefore be instructed to contact their health care provider(s) by telephone in cases of severe or concerning symptoms that arise between appointments, exactly as they would be instructed to do in the absence of WEBCORE use.
- A telephone number for technical assistance.

### 4.2.2 Clinician Training

Standardized training for participating MSKCC staff will be instituted prior to initiation of this protocol. In addition, a study investigator will be available during clinic visits to answer questions of staff, and to remind them of training points. Initial staff training will include:

- Showing applicable staff how to access and login to the WEBCORE administrative site using computers located in clinic.
- Explaining logoff procedures in order to assure the privacy of PHI.
- Demonstrating how to view and print WEBCORE Reports for participating patients, for use during clinic visits.
- Explaining to clinicians how to interpret WEBCORE Reports.
- Clarifying that printing WEBCORE Reports for inclusion with other visit materials is a mandatory part of this protocol, and must be done each time a participating patient has an appointment.
- Encouraging clinicians to discuss the results of WEBCORE reports with patients during visits.

## Memorial Sloan-Kettering Cancer Center IRB Protocol

**IRB#: 08-155A(8)**

### **4.2.3 Logging into WEBCORE**

Subjects are expected to login to WEBCORE once weekly from a home computer to fill out the online questionnaire. Subjects will be able to login to WEBCORE from any Internet-accessible computer whenever they wish to record symptoms, even if it is more frequently than the recommended weekly interval. Patients will be sent email reminders on the day they are due to login to WEBCORE which are identical to the email reminders currently in use in 04-020 (Appendix 10), and a follow-up email reminder email will be sent when they are overdue to login. Those who fail to respond to the follow-up email will receive a backup telephone call to administer the questionnaire and assess reasons for non-compliance.

Each time a patient logs in to the WEBCORE website, he or she will respond to items in the questionnaire, and these responses will be securely stored in the MSKCC Clinical Research Database (CRDB).

Technical assistance accessing the system will be available 24 hours. Patients will not be offered any financial incentives to login.

### **4.2.4 Generation of WEBCORE Reports at Outpatient Visits**

Based on information entered into WEBCORE and recorded in the WEBCORE database, it will be possible to generate summary “WEBCORE Reports” which track symptom trends over time for each patient who is assigned to use WEBCORE, in list or graphic form.

When a study participant comes for an office visit either during the study time period and/or for her first visiting following the end of the study period, her WEBCORE Report will be printed by clinic session assistants or an RSA. The report will then be added to other materials that are routinely reviewed by the nurse and/or gynecologic oncologist as a part of standard care (eg, laboratory test printouts, radiology results, procedure reports, or past clinic visit dictations). The Report printout will be the second page of these materials.

The technical functionality of WEBCORE will be designed such that information entered by patients just prior to clinic visits will be available immediately for printing in WEBCORE Reports (and thus for clinician review during that visit). Printing capabilities in the clinician work areas are readily available.

### **4.2.5 Warning Emails and Popup Messages**

If a patient self-reports a severe or disabling level of severity for any symptom(s) into WEBCORE an automated warning email flagged as “urgent” and titled “severe Patient-related symptom” will be sent in real-time to the research fellow, the designated RSA and the PI of the study. They will forward the email to the POA of the patient’s gynecologic oncologist and to the clinic nurse taking patient calls for that gynecologic oncologist that day. (This is the same system used presently to triage patient phone calls.) If the research fellow is not available,

**Memorial Sloan-Kettering Cancer Center  
IRB Protocol**

**IRB#: 08-155A(8)**

coverage will be provided by the designated RSA. In that event, the designated RSA will notify the POA of the patient's gynecologic oncologist and the clinic nurse taking patient calls for that gynecologic oncologist that day. No specific responses to these emails will be required, but any actions taken in response to these alerts by clinicians will be tracked (ie, telephone calls, supportive medication prescriptions, new appointments made, etc) using a form emailed to the nurse after the automated email alert (Appendix 5) and the "Ambulatory Care Phone/Email Communication Form" in the EMR. The forms will be collected by the research fellow or by the designated RSA. In addition, a warning popup message will advise the patient that WEBCORE information is not monitored in real-time and therefore to consider calling her physician's office about the symptom of concern.

## **5.0 CRITERIA FOR SUBJECT ELIGIBILITY**

### **5.1 Subject Inclusion Criteria**

- Participants must be 18 years or older.
- Participants must be able to provide informed consent.
- Participants must be scheduled to undergo laparotomy for presumed or known gynecologic cancer.
- The assessments were designed and validated in English and are not currently available in other languages. Translation of questionnaires into other languages would require reestablishing the reliability and validity of these measures. Therefore, participants must be able to communicate in English to complete the tests. Participants must be able to speak and read English fluently.
- Participants must have access to a home computer, have a personal email account, and check email at least once weekly by self-report

### **5.2 Subject Exclusion Criteria**

- Patients who have a cognitive or psychiatric deficit resulting in an inability to provide meaningful informed consent, as judged by the consenting professional, and/or as noted in the medical record.
- Patients who are undergoing pelvic exenterative surgery (with the exception of patients undergoing modified pelvic exenteration in the context of debulking for ovarian or uterine cancer).

**Memorial Sloan-Kettering Cancer Center  
IRB Protocol**

**IRB#: 08-155A(8)**

**6.0 RECRUITMENT PLAN**

The recruitment process will take place during office visits on the 6th floor of the MSKCC 53rd street outpatient clinic building. New patients, scheduled to undergo surgery, and consent visits, who are potentially eligible for the study will be identified by the treatment team. The investigator/ research staff of the study will be notified by the patient's treatment team.

After identifying potentially eligible patients the patients will be approached by the investigator/ research staff (Research Fellow and/ or Surgery RSA) either during the time of the initial visit or during the time of the consent for the surgical procedure. During the initial conversation between the investigator/research staff and the patient, the patient may be asked to provide certain health information that is necessary to the recruitment and enrollment process. The investigator/research staff may also review portions of their medical records at MSKCC in order to further assess eligibility. They will use the information provided by the patient and/or medical record to confirm that the patient is eligible and to inform the patient regarding study enrollment. If the patient turns out to be ineligible for the research study, the research staff will destroy all information collected on the patient during the initial conversation and medical records review, except for any information that must be maintained for screening log purposes (see Appendix 9).

**7.0 ASSESSMENT/EVALUATION PLAN**

**7.1 Baseline Information Questionnaire**

Variables that we expect may be predictors of WEBCORE utilization include age, education level, employment status, and prior Internet experience. These will be measured at baseline via a paper patient questionnaire (Appendix 1). This questionnaire will be administered by the consenting professional immediately after obtaining Informed Consent and Research Authorization. The paper questionnaire will be done at the time of the initial training session. Together, the training and the questionnaire will take 15 minutes.

**7.2 Demographic Data**

Basic demographic data, including age, race, American Society of Anesthesiologists Score (ASA), cancer type, stage of disease, current/planned therapy, procedure type, and details of any complications will be obtained by the research assistant or research fellow using the MSKCC electronic medical record.

**7.3 WEBCORE Questionnaire Items**

Based on expert consultation and literature review, questionnaires and items were selected to upload to WEBCORE for this study in order to focus on symptoms that may reflect general and specific post-operative complications, or which might cause distressing symptoms. The WEBCORE Questionnaire is a composition of items of validated instruments with a focus on postoperative symptom and QoL assessment.

These include a single-item assessments of symptoms using the patient-adaptation of

## Memorial Sloan-Kettering Cancer Center IRB Protocol

**IRB#: 08-155A(8)**

the NCI's CTCAE developed for prior WEBCORE studies [13]; and the well-established HRQL instrument, the European Organization for Research and Treatment of Cancer's QLQ-C30 [47]. Each validated instrument included in this protocol has undergone extensive prior psychometric testing and meets established standards for validity and reliability as detailed in the FDA Draft guidance for PROs [3, 5]. These questionnaires/items are described below:

The first question of the EORTC QLQ-30 version 3.0 is, "Do you have any trouble doing strenuous activities, like carrying a heavy shopping bag or a suitcase?" and the available responses are "not at all", "a little", "quite a bit" and "very much". However, post-operatively patients are instructed to avoid lifting anything heavy, like a shopping bag or suitcase, for at least 6 weeks after surgery. After consultation with experts, including the Behavioral and Psychosocial Research Consultation Program at MSKCC, the decision was made to preserve the integrity of the validated instrument and to instruct the patients to choose the response "very much".

**Memorial Sloan-Kettering Cancer Center  
IRB Protocol**

**IRB#: 08-155A(8)**

**7.3.2 Individual Symptom Items**

To assess symptoms not addressed within the QLQ-C30, individual items will be included for symptoms of potential concern in the post-operative period. These symptoms were chosen based on expert consultation and literature search, and include general postoperative symptoms such as pain, fever, shortness of breath, surgical wound symptoms, nausea and vomiting, bowel function, fatigue as well as more specific gynecologic symptoms such as dysuria, urinary retention, and finally cardiac, cardio-vascular and pulmonary symptoms. These will be assessed via patient adaptations of NCI CTCAE items [13].

**7.4 Patient Satisfaction**

Patient assessment of the usefulness of WEBCORE will be measured via an exit questionnaire (Appendix 2) available on WEBCORE 6 to 8 weeks after surgery. Items in this questionnaire are adapted from validated measures used in prior studies evaluating satisfaction with information technology interventions [50-54] and instruments developed by the Picker Institute [55], and makes use of an ordinal scale for recording responses. Questions address two specific areas: ease of use (ease of login, ease of data entry, understandability of questions), and perceived usefulness (memory triggering, use of information by doctors/nurses, feeling of control over own care, feeling that care was improved).

**7.5 Clinician Evaluation of WEBCORE**

**7.5.1 Nurse Intervention Report**

If a patient submits a response that is concerning according to pre-specified limits set by the gynecologic oncology service, an automated email alert flagged as “urgent” and titled “sever Patient-reported symptom” will be sent in real-time to the research fellow, the designated RSA and the PI of the study. They will forward the email to the POA of the patient’s gynecologic oncologist and to the clinic nurse taking patient calls for that gynecologic oncologist that day. (This is the same system used presently to triage patient phone calls.) If the research fellow is not available, coverage will be provided by the designated RSA. In that event, the designated RSA will notify the POA of the patient’s gynecologic oncologist and the clinic nurse taking patient calls for that gynecologic oncologist that day. No specific responses to these emails will be required, but any actions taken in response to these alerts by clinicians will be tracked (ie, telephone calls, supportive medication prescriptions, new appointments made, etc) using a form emailed to the nurse after the automated email alert (Appendix 5) and the “Ambulatory Care Phone/Email Communication Form” in the EMR. The forms will be collected by the research fellow or by the designated RSA. The form will list the patient’s name, diagnosis, date of surgery, surgery and the symptom(s)

## Memorial Sloan-Kettering Cancer Center IRB Protocol

**IRB#: 08-155A(8)**

that triggered the alert. The form will take approximately 5 minutes to fill out. If the nurse indicates that a patient was contacted as a result of the automated email, the research fellow or RSA will look at the “Ambulatory Care Phone/Email Communication Form” in the EMR and record what action was taken. Forms will be collected by the research fellow or RSA. Possible responses include: diagnostic test, prescription, office visit scheduled, UCC visit recommended, no action, other.

### **7.5.2 Clinician Group Meeting Questions: Focus Group**

At the completion of the study period, a focus group will be scheduled with all clinicians and support personnel involved in the care of enrolled patients (physicians, nurses, Session Assistants). Specific open-ended questions will be asked verbally to assess qualitative impressions of WEBCORE, and to obtain suggestions for future development of WEBCORE (Appendix 6). Questions will include whether WEBCORE was felt to be useful overall, not useful, or detrimental; whether it saved or consumed time; whether summary reports should be used to replace other assessment documents in the patient chart; and whether clinicians feel that patient self-generated reports accurately depict levels of toxicity.

### **7.5.3 Clinician Satisfaction**

At the completion of the study, nurses and physicians will be emailed a survey to evaluate clinician satisfaction, strengths and weaknesses of WEBCORE (Appendix 8). It will take 10 minutes to complete.

## **8.0 TOXICITIES/SIDE EFFECTS**

Minimal risk of psychological distress is posed by study questions that ask participants to identify their current problems. However, since study items were chosen to reflect what are likely to be existing concerns, the present study is not expected to markedly increase participants' psychological distress above their routine concerns. WEBCORE allows a participant to skip any question(s) that she chooses, without compromising her ability to complete the rest of the questionnaire. Formal testing of depression is not included as part of the questionnaire, however, if a patient responds “quite a bit” or “very much” to the question, “Did you feel depressed?”, an automatic email alert will be sent to the clinic nurse and the research fellow, who will follow up with the patient. In addition, any patient who communicates distress to the RSA or research fellow verbally will be referred for counseling. In the unlikely event of significant acute distress, participants will be referred to a staff member from the Department of Psychiatry and Behavioral Sciences. If a research participant indicates that s/he is acutely suicidal and poses a significant and acute risk of self-harm, this information will be shared with their attending physician so that timely and appropriate psychiatric assessment and care can be provided by the MSKCC

**Memorial Sloan-Kettering Cancer Center  
IRB Protocol**

**IRB#: 08-155A(8)**

Social Work or Psychiatry Service staff. There is no guarantee of benefit to participants based on study participation. Participants can withdraw from the study at any time.

## **9.0 PRIMARY AND SECONDARY OUTCOMES**

### **9.1 Primary Outcome**

The primary objective of this study is to evaluate the feasibility of patients using WEBCORE to track their own symptoms and HRQL while recovering from laparotomy for presumed or confirmed gynecologic cancer. In this pilot feasibility study, we will measure several parameters related to patients' utilization of the WEBCORE system, in order to evaluate the potential for implementation of collecting patient self-reported measures in a gynecologic oncology practice and/or in clinical trials.

- To gauge patients' willingness to record their experiences we will record the ratio of the number of patients approached for study participation to the number who enroll. The proportion of patients approached versus consented will be tracked continuously by the Research Fellow and the designated Surgery RSA.
- We will evaluate the extent to which patients who enroll in the protocol use the WEBCORE system to self-report symptoms and HRQL. Specifically, we will measure how often each user accesses the WEBCORE system, and will note the time and date that utilization occurs. Perfect compliance would be logging on and completing all the questions seven times: once pre-operatively, and then weekly for six weeks following surgery. In keeping with standards for the assessment of feasibility of online platforms, as a crude measure of feasibility, we will consider the study results to suggest that WEBCORE is a strategy warranting larger scale evaluation if approximately 80% of participants login to WEBCORE at least four times during the study period [13]. In our analysis, we will look at WEBCORE utilization (1) over time and (2) in relation to the presence or absence of documented minor and major surgical complications. The proportion of users who logged in with or without a follow-up reminder email will be tabulated. We will assess for attrition of compliance over time by measuring the proportion of patients who login during each consecutive week of observation.
- Results of backup telephone calls made when patients have not logged in will be tabulated to assess if the reported symptoms of such patients differ from reports of patients who have logged in on time, and reasons for non-compliance.
- Variables that we expect may affect levels of utilization include cancer type diagnosis, procedure type, age, education level, employment status, prior Internet experience, baseline ASA score and baseline HRQL. Therefore, these will be measured at baseline via a questionnaire (Appendix 1), chart review, and by the patient's initial score on the EORTC QLQ-C30 when she logs in pre-operatively.

**Memorial Sloan-Kettering Cancer Center  
IRB Protocol**

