## Memorial Sloan-Kettering Cancer Center IRB Protocol

**IRB#: 08-155A(8)**

Based on prior MSKCC research in this population, we anticipate that 90% of approached patients will agree to participate, of which 75% will be regular email users [13]. We will track the proportion of patients approached who consent as one of the measures of feasibility. The proportion of patients approached versus consented will be tracked continuously by the Research Fellow and the designated Surgery RSA. There are approximately 570 laparotomies performed on the gynecology service annually (internal data). We anticipate that accrual for the study will be complete within 6-9 months. We will enroll the first 5 patients of 110 patients as a small pilot to identify potential problems and correct any issues that may arise. After the evaluation of the first 5 patients the accrual period will remain open until at least 80 evaluable patients are enrolled. The sequence of patient activities following accrual is shown in Figure 1.

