## Memorial Sloan-Kettering Cancer Center IRB Protocol

**IRB#: 08-155A(8)**

### 13.1 Quality Assurance

Weekly registration reports will be generated to monitor patient accruals and completeness of registration data. Routine data quality reports will be generated to assess missing data and inconsistencies. A log of all eligible patients will be maintained. Accrual rates and extent and accuracy of evaluations and follow-up will be monitored periodically throughout the study period and potential problems will be brought to the attention of the study team for discussion and action.

Random-sample data quality and protocol compliance audits will be conducted by the study team, at a minimum of two times per year, more frequently if indicated.

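### The willingness measure in Section 9.1 counts patients found ineligible after approach, for example for lack of email use, the same as patients who refuse

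*Combined protocol and SAP*

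**What the plan says.** Under the primary outcome, Section 9.1 lists first a measure of patients' willingness to record their experiences: "the ratio of the number of patients approached for study participation to the number who enroll". Section 11.1 adds a companion figure: "We will track the proportion of patients approached who consent as one of the measures of feasibility". Neither restricts the denominator to eligible patients.

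Section 5.1 makes computer access and email use conditions of entry: "Participants must have access to a home computer, have a personal email account, and check email at least once weekly by self-report".

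Section 6.0 sets the order of events. The treatment team identifies potential candidates, and then: "After identifying potentially eligible patients the patients will be approached by the investigator/ research staff". Eligibility is confirmed from that conversation and from the medical record. The section provides for those who fail: "If the patient turns out to be ineligible for the research study, the research staff will destroy all information collected on the patient", apart from what the screening log must keep. Section 12.1 lists confirming eligibility ahead of obtaining consent.

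Section 11.1 gives the expected yield: "we anticipate that 90% of approached patients will agree to participate, of which 75% will be regular email users".

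Section 11.2 plans two ratios with responders as numerator, one over enrollees and one over eligible patients, and compares baseline characteristics of refusers with those of patients who agree. On the data source, Section 13.1 says: "A log of all eligible patients will be maintained".

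**The concern.** A measure of willingness should fall when eligible patients decline and should not move for other reasons. The ratio in Section 9.1 also falls when approached patients turn out not to qualify. Because email use is by self-report and is checked after the approach, a patient who would gladly take part but does not check email weekly is recorded in the same way as one who says no.

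The two cases call for different next steps. Low willingness would question whether patients recovering from laparotomy accept self-reporting at all. Low email access would point to other modes of collection. Section 3.7 foresees backup methods for patients who are unable or unwilling to complete electronic questionnaires, and a single approached-to-enrolled ratio cannot tell those groups apart.

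**Working it through.** The plan states no expected value for the willingness ratio, so there is no figure to reproduce. The inputs are from Section 11.1: 90% of approached patients agree, and 75% of those who agree use email regularly.

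**Per 100 approached**
- Agree: 100 x 0.90 = 90.
- Agree and meet the email criterion, so can enroll: 90 x 0.75 = 67.5.
- Agree but cannot enroll for lack of email use: 90 - 67.5 = 22.5.
- Refuse: 100 - 90 = 10.

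**The measure as written**
- Enrolled/approached = 67.5/100 = 67.5%. In the orientation of Section 9.1, 1/0.675 = 1.48 approached per enrollee.
- Agreement is 90%, or 1/0.90 = 1.11 approached per patient who agrees.
- Gap: 90 - 67.5 = 22.5 percentage points.
- Of the 32.5 approached patients who do not enroll, 22.5 (22.5/32.5 = 69%) had agreed.
- With a 75% email share, the measure could not exceed 75% even if every approached patient were willing.

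**The measure with an eligible denominator**
- The plan gives no email share among refusers. Call it s. Eligible approached = 67.5 + 10s.
- If s = 0.75, as among those who agree: 67.5/(67.5 + 7.5) = 67.5/75 = 90%, which recovers the anticipated agreement.
- Extremes: s = 1 gives 67.5/77.5 = 87.1%; s = 0 gives 67.5/67.5 = 100%.
- Over the whole range the eligible-based figure lies above 67.5%, by 19.6 to 32.5 points.

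**Dependence on the email share, with agreement held at 90%**
- 75%: 0.90 x 0.75 = 67.5%.
- 90%: 0.90 x 0.90 = 81%.
- 100%: 0.90 x 1.00 = 90%.

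The measure equals willingness only when every approached patient is eligible. Any ineligible patient in the denominator lowers it.

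**What Section 11.2 already allows**
- (responders/eligible) / (responders/enrollees) = enrollees/eligible.
- The two planned ratios together therefore imply an eligible-based enrollment rate. Section 11.2 does not say whether its eligible count is limited to patients who were approached.

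**The case against.** The strongest reply is that the plan nearly has the right quantity already. The two responder ratios in Section 11.2 yield enrollees over eligible by division, and comparing refusers with those who agree requires refusers to be identified as a group. Together with the log of eligible patients, this means refusal and ineligibility can be separated. That stands. A reader might infer that the study has no way to tell the two apart, and the documents do not support that. What remains is that the derived ratio is nowhere named as the willingness measure, while the ratio that is so named mixes the two.

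A second reply concerns the consent proportion in Section 11.1. If consent there means agreement before the email check, the figure would be near 90% and no gap arises. That reading is possible for the companion figure. It fits poorly with Section 12.1, which puts eligibility before consent, and it does not help Section 9.1, which counts enrollment.

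Third, the treatment team might screen for email before the approach. Section 6.0 speaks only of potential eligibility, and Section 11.1 applies its 75% to patients who have already been approached and have agreed, so the plan does not appear to assume this.

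Fourth, yield from everyone approached is informative about implementation. That is right, and is a reason to keep the ratio under another name.

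Two stronger readings are tempting. One is that a flaw in the first listed primary-outcome parameter undermines the feasibility conclusion. It does not: the decision rests on the responder count of 58/79, and the willingness ratio has no threshold or test. The other is to enlarge the gap by using the 60% email use in the gynecologic column of Table 2. That figure comes from an informal 2003 survey with 30 gynecologic patients, in a table titled for outpatients receiving chemotherapy. This trial enrolls patients scheduled for laparotomy, and Section 11.1 gives its own figure for them.

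**Conclusion.** The point holds as a minor correction to a descriptive measure. As defined, the Section 9.1 ratio understates willingness whenever an approached patient proves ineligible. On the plan's own expectations it would read about 67.5% against 90% agreement, a gap of 22.5 points. That size assumes that the 90% and 75% are borne out, that email use is the only source of ineligibility, and, for the eligible-based figure to equal 90%, that refusers use email as often as those who agree. The direction needs none of these. The feasibility decision is untouched.

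**What to change.** In Sections 9.1 and 11.1, define willingness as enrolled patients divided by approached patients who meet Sections 5.1 and 5.2, with a 95% confidence interval. Keep enrolled/approached, described as a measure of reach. Report the number of approached patients found ineligible, by reason (for example no home computer, no personal email account, email not checked weekly), separately from refusals.

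The cost is wording plus one check. The eligible-patient log in Section 13.1 supports the denominator, but the fields of the screening form (Appendix 9) are not shown in the text available, and Section 6.0 has other information on ineligible patients destroyed. The sponsor should confirm that the form and log keep four items: approach, eligibility, reason for ineligibility, and refusal. If any is missing it should be added, because the split may not be recoverable later.
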